8 INTERVENTION AND CONTROL

8.1 CONTROL GROUP

Patients will receive medical attention according to usual medical/surgical treatment and the peculiarities of each pathology and clinical setting. In this Group of patients a Comprehensive Geriatric Assessment will be done at hospital admission and discharge. If at any case, a geriatrician consultation is required, it should be registered in the eCRF and in patient's record. The statistical analysis of these patients' data should be made, if there's enough sample throughout a sensitivity analysis.

8.2 INTERVENTION GROUP

Patients included in this Group will be treated by usual physician with the support of geriatrics team, who will do Comprehensive Geriatric Assessment to detect any problem in the elderly population in the clinical, functional, mental and social domains. The objective is to establish a strategy of intervention, treatment and follow-up to optimize resources and improve independency and quality of life..

9 ASSESSMENTS DURING THE STUDY

9.1 BASELINE EVALUATION (visit 0= FIRST VISIT)

After the inclusion of a participant in the study, a comprehensive geriatric assessment will be done with the following parts:

Demographics and epidemiology: Date of birth, age, sex, race, caregiver, marital status, number of persons in the house, and, number of hospitalization in the last year, follow up by others specialist, level of education.

- Medical history

Personal Medical and Surgery History should be recorded in the electronic Case Report Form (eCRF).

- Medications:

In the CRF we register all the regularly medication use (previous hospitalization)

- Functional status

Evaluate functional status with the following scales: Barthel Index, Lawton Index, measures based in performance (SPPB-Short Physical Performance Battery) and PASE Scale, Annex 2.

- Cognitive and depression:

Evaluate the results with MMSE and Geriatric Depression Scale GDS, and delirium risk with CAM scale. See Index 2.

- Physical examination:

Vital signs and physical examination as usual by the clinical investigator.

- Geriatric Syndromes Assessment:

Immobility: Falls and imbalance.

Incontinence: urinary and fecal.

Sensory deprivation

Iatrogenic: Record the numbers of falls during the hospitalization and adverse effects

Pain: assess pain using the VAS Scale. Nutritional Status:

Performed screening for nutritional status using the scale MNA (Mini Nutritional Assessment), Index 2.

- Comorbidities:

Comorbidities will be quantified by Charlson Index, Index 2.

Quality of Life :

The evaluation for the quality of life using the EuroQol five-dimensional (EQ-5D), Index 2.

Caregiver :

- Assessment for the burden of the caregiver; Will be evaluated with The Modified Caregiver Strain Scale. Index 2.

9.2 EVALUATION AT DISCHARGE FROM THE SPECIFIC CLINICAL SETTING

The following aspects will be assessed:

- Mortality
- Frailty assessment with L. P. Fried's scale and/or FRAIL scale. Functionality assessment with Barthel Index. Indicate the number of hospital stay in days .
- Describe if the patient change the Ward location/ medical /surgical in the hospital (UCI, Coronary unitetc) o)during the evolution in the hospital
- Quantification the number of test (Blood test, urine test, X- Ray, ecography, CT, etc and more specialized like: PET TAC, echocardiography, polisomnography, etc.)
- Quantification the number of consult with other specialist, social worker, palliative care. Etc.
- Usual treatment (Register all the medication at discharge
- Evaluate if the patient develop geriatric síndrome (page 22).
- Destination at dischargeia. (Nursing home, follow up by home care team, I HUG- GRT, day hospital, rehabilitation at home , specialist consultation, etc.)
- Evaluate the perception of the quality of life with the scale EuroQol five-dimensional (EQ-5D).
- Burden of the caregiver with the Economics questionnaire s.
- Economics evaluation Index 3

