4 OUTCOMES

4.1 PRIMARY OUTCOMES:

1. **Disability:** It was measured by the Barthel Index for basic Activities of Daily Living and the Lawton index for instrumental activities of daily living.
2. **Functional status and performance-based measures:** Functional status and performance-based measures: Is measured by Short Physical Performance Battery (SPPB), Physical Activity Scale for the Elderly (PASE SCALE).
3. **Quality of Life:** Quality of life was assessed by self-reported questionnaire EuroQL 5D 5L. It will be measured during admission to hospital and follow-up.
4. **Geriatrician Intervention:** The impact of their intervention is measured by quantifying in a register any additional tests requested and medical advice by other specialists.

4.2 SECONDARY OUTCOMES:

Prevalence of Delirium: The delirium cases are detected by Confusion Assessment Method (CAM) scale.

Cognitive Impairment: Will be measured by the Mini Mental State Examination (MMSE) in the initial assessment.

Depression: will be assessed using the Geriatric Depression Scale in the baseline assessment.

Health-care associated infections: Acquired during hospitalization start.

Geriatric Syndromes: The geriatric evaluation including the following aspects: clinical, functional, mental and social.

Comorbidity: Will measured at initial assessment thorough Charlson index

Nutritional Status: Will measured at initial assessment thorough the Mini Nutritional Assessment and body Mass index.

Polypharmacy: Defined as five or more prescription drugs.

Mortality rate: Number of deaths during follow-up. It is calculated using official report of the National Statistics Institute (INE).

Average stay hospitalization: Average length of stay of stay all discharges. We will obtain from Hospital Admissions service.

Hospitalization Rate in Emergency room: Number of hospital admissions over the total of patients admitted in the hospital.

Readmission rates: Number of readmissions during of follow-up period. I will get the data in Hospital Admissions Service.

Institutionalization: Number of patients referred to nursing home after discharge or at any time during follow-up. This information is obtained directly from patients or their relatives.

Requirement of caregiver: Number of patients who require a caregiver after hospital discharge.

Caregiver burden: Will be used Zarit Scale for assessing caregiver burden

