7.2 RANDOMIZATION

After verification that the participant fulfils the eligibility criteria and signed the informed consent, allocation will be made to a control or/an intervention group.

Participants will be randomized 1:1 through the eCRF by Linkcare Company, which also will do the database.

Patient's participation in the study and the telephone number of the study contacts will always be registered in his/her clinical record.

According to the study's schedule, the intervention phase will start the sixteenth week, taking into account the adjustments of the ethics committee in each country. Follow-up will be made at hospital discharge and at the third and sixth month after discharge.

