9.5 END OF THE STUDY EVALUATION

- The study will finish at 12 months after patient's discharge with a lastphone call .
- We should make an effort to write all the data during the study, at follow up and the final evaluation..

A follow-up and investigator's tasks schedule was performed during the study. See table 2.

Table 2 Schedule of the investigation

Intervention phase	Eligibility&recruitment	Initial Visit	Discharge	3 month Follow-up	12 month Follow-up
Informed consent	X				
Eligibility CI and CE	X	X			
Medical history		X			
Usual treatment		X	X	X	X
Comprehensive Geriatric Assessment		X			
Cognitive and depression (MMSE,GDS,CAM)		X			
Comorbidities - Charlson I.		X			
Functional Status (Barthel I, Lawton I, PASE, SPBB)		X SPBB	X Barthel	X	X
Sociodemographic data		X			
Physical Exam		X			
Nutritional Status (MNA)		X			
Permanent residence		X	X	X	X
Mean hospital stay			X		
Death			X	X	X
Frailty (Fried)		X	X		
Frailty(FRAIL)		X	X	X	X
EuroQolfive-dimensional (EQ-5D)		X	X	X	X
Caregiver burden		X	X	X	X
Relocation to other hospital services			X		
Adverse events (iatrogenic, falls, geriatric syndromes, etc.)		X	X		
Economics evaluation			X	X	X
Checklist of complementary test during the hospitalization			X		
Consultation to other specialist during hospitalization			X		

Coordination of care in different levels of care		X		
Readmission			X	X
Visits to the emergency room			X	X
Nosocomial infections		X		

* In case of surgical patients, who after 3 weeks since the first visit have passed and surgery hasn't been performed, evaluate the possibility of re-assessing inclusion criteria.

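### In-hospital days, tests and consultations are not counted from randomisation, so for patients randomised after admission the totals include time the intervention could not affect, at a cost in precision.

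*Combined protocol and SAP*

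**What the plan says.** **Allocation.** Section 7.2: "After verification that the participant fulfils the eligibility criteria and signed the informed consent, allocation will be made to a control or/an intervention group". Eligibility (section 6) needs a frailty diagnosis, MMSE, GDS and Barthel scores, and judgements on intensive care need and life expectancy. No maximum interval from hospital admission is set.

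**Length of stay.** Section 9.2 asks at discharge: "Indicate the number of hospital stay in days". Section 4.2 defines the outcome as "Average length of stay of stay all discharges. We will obtain from Hospital Admissions service". Neither gives a start point.

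**Tests and consultations.** Table 2 has the rows "Checklist of complementary test during the hospitalization" and "Consultation to other specialist during hospitalization", each marked at discharge only. They correspond to primary outcome 4 in section 4.1, which speaks of *additional* tests and advice from other specialists, kept in a register.

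**Falls and adverse effects.** Section 9.1, the baseline visit, says "Record the numbers of falls during the hospitalization and adverse effects". Table 2 marks adverse events at the initial visit and again at discharge.

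**Analysis.** Section 7.4 names a Mann-Whitney test between arms. It gives no start date, offset or baseline adjustment for these outcomes.

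**The concern.** Emergency and unplanned ward patients will usually have spent some time in hospital, and had some of their admission work-up, before they can be screened, consented and allocated. That part of the stay is alike in the two arms on average, because it precedes allocation. Including it adds a common component to both arms. The contrast is unchanged on the difference scale, smaller on the ratio scale, and measured with more noise on either.

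The outcomes touched are primary outcome 4, length of stay, possibly falls, adverse events and nosocomial infections, and the cost-effectiveness analyses in section 10 that use them. Section 7.3 plans 155 per arm in each clinical setting, and the interval before randomisation is likely to vary by setting. The loss would therefore fall unevenly on the per-setting comparisons and on the meta-analysis across settings.

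**Working it through.** **Inputs from the documents.** 155 per arm per setting, 20% dropout and 40% disability incidence (section 7.3); 1:1 allocation (section 7.2); Mann-Whitney test (section 7.4).

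**Assumed, because the documents give nothing.** Stay after randomisation in controls is lognormal with mean 8 and SD 7 days. The true ratio is 0.80, a difference of 8 × 0.20 = 1.6 days. Days before randomisation are exponential with mean *m* in both arms. The share of control events before randomisation is *s*.

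**The plan's own figure.** The smallest n with 0.4n − 1.96√(0.24n) ≥ 40 is 128, where the bound is 40.3. Then 128 × 1.2 = 153.6, rounded up to 154, which is close to the stated 155 (128/0.8 would give 160). This calculation concerns disability. The plan has no sample-size figure for days, tests or consultations.

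**Ratios of counts.** Observed ratio = s + (1 − s) × 0.80.
- s = 0.10: 0.10 + 0.72 = 0.82
- s = 0.25: 0.25 + 0.60 = 0.85
- s = 0.50: 0.50 + 0.40 = 0.90

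**Any-event risk.** Assume 20% against 10% after randomisation and a 5% risk before it, all counted together. The risks become 1 − 0.95 × 0.80 = 0.240 and 1 − 0.95 × 0.90 = 0.145. The risk ratio is 0.60 instead of 0.50, and the risk difference 0.095 instead of 0.100.

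**Length of stay.** Difference = (8 + m) − (6.4 + m) = 1.6 days for every m. Ratio = (6.4 + m)/(8 + m). Power is from simulation (Mann-Whitney, two-sided 5%, 155 per arm) and is good to about 0.02.

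| Mean earlier days, m | Ratio | Power |
|---|---|---|
| 0 (count from randomisation) | 0.80 | 0.72 |
| 0.5 | 6.9/8.5 = 0.81 | 0.70 to 0.72 |
| 1 | 7.4/9 = 0.82 | 0.68 |
| 2 | 8.4/10 = 0.84 | 0.61 |
| 4 | 10.4/12 = 0.87 | 0.50 |

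At 155 × 0.8 = 124 per arm, after dropout, power goes from about 0.62 to 0.58, 0.53 and 0.40 for m = 1, 2 and 4. A gamma model with mean 8 and SD 6 gives the same pattern at 155 per arm: 0.66, then 0.65, 0.61 and 0.51. With all settings pooled (1860 × 0.8/2 = 744 per arm), that gamma model keeps power at 0.986 or more even at m = 4.

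No power is given for counts of tests. It would depend on their mean, overdispersion and within-patient correlation, none of which the documents supply.

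**The case against.** **No passage says outright that time before randomisation is included.** This is true. It is inferred from the whole-stay windows, the administrative source and the absence of a start rule. For tests and consultations the wording is fairly plain. For stay, a figure from the admissions service is most naturally read as running from admission.

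**The interval may be short.** Section 8.1 places the control group's geriatric assessment at hospital admission. If allocation happens then too, the loss is negligible, as the row for half a day shows. Nothing in the plan enforces this.

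**Outcome 4 says *additional*.** That can be read as tests arising once the geriatrician is involved. The word is undefined, and the data described in section 9.2 and Table 2 are single discharge totals. The objection narrows the point without removing it.

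**Falls already have a baseline record.** This is also true, and the two records could separate earlier from later falls. The plan does not say that they will be used that way.

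**Admission-to-discharge stay is a legitimate outcome.** It is. A reader might infer that whole-stay counting biases the treatment comparison or shrinks the cost difference. The documents do not support that. Earlier time is balanced in expectation, and the cost numerator in section 10 is a difference between arms, so it gains variance only.

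**Counting literally from randomisation could do harm.** This stands, and it shapes the remedy. Elective surgery is listed at five of the six hospitals in Table 1, and the footnote to Table 2 foresees more than three weeks between first visit and surgery. Some of these patients may be randomised before admission, and waiting time would then enter the stay. With assumed uniform waits of 0 to 7, 0 to 14 or 0 to 21 days, power falls from 0.72 to about 0.59, 0.42 or 0.30.

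**Conclusion.** The point holds as a loss of precision and as attenuation of ratios and any-event risks, for patients randomised after admission. At 155 per arm, the assumed stay model loses about 4, 11 and 22 percentage points of power with a mean of 1, 2 and 4 earlier days, and almost nothing at half a day. A true ratio of 0.80 reads 0.82 to 0.90 when 10% to 50% of control events come first. The stay model, the number of earlier days and the share of earlier events are all assumptions, and the real values could be smaller.

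A reader might also infer that the trial's main comparison is weakened throughout. It is not. Disability, on which the sample size rests, is untouched, and pooled stay power barely moves. The matter is nonetheless worth settling before data collection, because a single discharge total of tests or consultations cannot be split afterwards without going back to the charts.

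**What to change.** In section 4.1 (outcome 4), section 4.2, section 9.2 and Table 2:

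- Count in-hospital days, tests, consultations, falls, adverse events and nosocomial infections from the later of hospital admission and randomisation, up to discharge. The words *later of* keep waiting time out of the stay of patients randomised before admission.
- Record the date and time of admission and of randomisation in the eCRF, through which allocation already runs ("Participants will be randomized 1:1 through the eCRF").
- State that the visit 0 record of falls and adverse events covers the time before randomisation, and the discharge record the time after it.
- Use earlier days and counts only as baseline covariates. Report whole-stay totals and whole-stay cost descriptively.

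**Cost.** The wording changes and the two time fields are minor. The real burden is that site staff must split tests and consultations at the randomisation time when they complete the checklist.

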9.3 EVALUATION AT 3 MONTHS OF DISCHARGE

Re-evaluate the following aspects by phone :

- Mortality
- Functionality data (Barthel index , Lawton index , PASE Scale).
- Usual medication.
- Residency at the moment.
- Frailty with the FRAIL scale..
- Data of quality of life with the scale EuroQolfive-dimensional (EQ-5D)
- Number of hospitalization and ER, indicate the cause (diagnosis)
- Caregiver burden with the economic questionaries .
- Economics evaluation, Index 3

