Complementing the main cost-effectiveness analysis, we will develop several parallel cost effectiveness analysis to the extent that effective change. The results that we will use are: hospitalization rate and readmission, lenght of hospitalization and in the Emergency department, episodes of delirium and nosocomial infection, post-surgical complications as a whole and by surgical procedure, number of inappropriate drugs, adherence to treatment, permanent institutionalization rate, survival rate, preventable side effects due to under / over / mismanagement on caregiver burden.

Cost-utility analysis:

Cost-utility analysis (ACU) is an evolution of cost-effectiveness analysis, in which the interference effects are measured in a unit that synthesizes the lifespan and quality of life. The best and better known measure is the quality of life-adjusted per quality (QALY QALY or in its Anglo-Saxon sense). The QALYs are calculated by weighting the survival time (years of age) with quality adjustment thereof, called utility, which represents the preference values in relation to different health states (reference). For the purpose, the EQ-5D-5L instrument will be used. The incremental cost-utility relation answers the following expression:

$$\text{ACU}_{\text{incremental}} = (C_a - C_b) / (\text{AVAC}(a) - \text{AVAC}(b))$$

Statistical analysis:

A descriptive analysis of the main resources used in health care, social services and informal care will be performed.

This includes basic statistics such as means, medians, standard deviations, skewness, kurtosis, ranges, bivariate analysis using different cost elements and individual characteristics (sex, age,...) and health outcomes.

Because different distributions are expected from major cost components, we hope to develop different multivariate estimation methods. As we expect a non-normal distribution of the estimated costs, an alternative analysis would be the use of GLM models grouped by clusters, where depending on the distribution of the estimated costs (distribution Gamma, Poisson or Gaussian), will be used the most suitable method of empirical analysis. Another alternative, if the necessary information is obtained, could be an analysis using multilevel models of 2 or 3 grade (Recital country and center). The costs

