b. **In the case of yes, who is your principal carer?**

- Family member ⇒ Fill in the carer questionnaire and skip to question #6
- Another non-contracted person (friend) ⇒ Fill in the carer questionnaire and skip to question #6
- Professional carer (contracted or provided by an entity)

c. **If you use the services of a professional carer,**

How many hours a week? _____ hours a week

Who pays for the service and how much?

- I pay the entire cost of _____ € per hour

(Alternative, if the subject does not know the cost per hour)

- I pay the entire cost of _____ € per month
- The cost is covered by social security or another entity
- The cost is partially covered by social security or another entity, I pay _____ € per hour

(Alternative, if the subject does not know the cost per hour)

- The cost is partially covered by social security or another entity, I pay _____ € per month

6. Hospitalisation

Have you been admitted to hospital in the last 12 months?

- Yes
- No

7. Health and social services you have required and days of service received by according to economic system during the last month and the last 6 months.

Mark the services you have required, number of days received and form of payment. In case you have required a service and have not received it, note the reason number (see the possible reasons below the table).

Kinds of services	You have needed to receive..	Days service received according to economic system			Reason for which they have not received the service (*)
		Free of charge	Direct payment	Mixed (public and private)	
During the last month...		During the last month...			
1. Telecare		— days	— days	— days	

2. Domiciliary care /help		— days	— days	— days	
3. Day centre		— days	— days	— days	
4. Occupational centre or centre for cultural, recreational and leisure activities		— days	— days	— days	
5. Other:		— days	— days	— days	
In the last 6 months...		In the last 6 months...			
6. Respite services: Temporary stays		— days	— days	— days	
7. Residential centres		— days	— days	— days	
8. Other:		— days	— days	— days	

(*) Reasons: 1 – Waiting list. 2 – Not available in the setting. 3 – Cannot pay it. 4 – Does not comply with any of the requirements. 5 – Other reasons.

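### Institutionalisation is defined as a nursing-home move at any time in follow-up, but after discharge only current residence at two phone calls is scheduled, so stays that start and end between contacts can be missed.

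*Combined protocol and SAP*

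**What the plan says.** Section 4.2 lists institutionalisation as a secondary outcome and counts "Number of patients referred to nursing home after discharge or at any time during follow-up". On the source it adds: "This information is obtained directly from patients or their relatives".

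The collection items are these:

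- **Section 9.2, discharge:** the destination is recorded, with nursing home as an option ("Destination at dischargeia. (Nursing home, follow up by home care team").
- **Sections 9.3 and 9.4, phone calls at 3 and 12 months:** the residence item is "Residency at the moment".
- **Table 2 (section 9.5):** the row is called "Permanent residence" and is marked at the initial visit, discharge, 3 months and 12 months.
- **Section 10:** one of the parallel cost-effectiveness outcomes is the "permanent institutionalization rate".
- **Annex 3 (section 11):** the subject questionnaire, headed as a baseline form, asks for days in "Residential centres". The form covers services "during the last month and the last 6 months", and this item falls under the six-month look-back. The week 12 and week 52 forms shown are for carers and contain no such item.

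Section 6.2 excludes nursing-home residents, so any nursing-home stay after enrolment is a new event.

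**The concern.** The outcome covers a period, while the scheduled item records a state on two days. The same calls ask for hospital admissions and emergency visits as counts with causes, but residence only as a status. For a patient who has died, current residence has no answer, and no item asks where the patient had been living.

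Three different variables therefore share one outcome name: any move during follow-up (4.2), residence on the day of the call (9.3, 9.4) and permanent residence or placement (Table 2, section 10). An analyst could report any of them. If the scheduled item is used, the 4.2 outcome is undercounted, and the undercount depends on mortality and on returns home, both of which the intervention might change.

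**Working it through.** The plan states no rate, effect size or power for institutionalisation, so there is no figure to reproduce. The check compares the definition with the items, then sizes the gap under stated assumptions.

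**Definition against collection**

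| Type of nursing-home stay | Counts under 4.2 | Scheduled item that would show it |
|---|---|---|
| Move directly at discharge | Yes | Discharge destination (9.2) |
| Entry after discharge, still there at month 3 or 12 | Yes | Current residence (9.3, 9.4) |
| Entry and return home between contacts | Yes | None |
| Entry, then death before the next call | Yes | None |

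The longest uncovered interval is 12 − 3 = 9 months. Section 7.2 instead sets follow-up at the third and sixth month, which would make it 3 months. The two sections must be reconciled.

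**Assumptions (none from the documents)**

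- Entry to a nursing home from the community: 10% a year.
- Discharged directly to a nursing home: 5%.
- Twelve-month mortality in the community: 15–30%, with the hazard doubled in a nursing home.
- Return home: 0, 3 or 8% a month.

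A 12-month probability q becomes a monthly hazard h = −ln(1 − q)/12. Entry at 10% gives 0.00878. Mortality at 20% gives 0.01860, doubled to 0.03719 in a nursing home.

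**Later moves only (simple check)**

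Suppose entry is uniform over the 9 months between calls and re-entry is ignored. With exit hazard k (death plus return), the share no longer in the nursing home at month 12 is 1 − (1 − e^(−9k))/(9k).

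- Low: 15% mortality, no return. k = 0.0271, 9k = 0.244; 1 − (1 − 0.784)/0.244 = 11%.
- Middle: 20% mortality, 3% return. k = 0.0372 + 0.03 = 0.0672, 9k = 0.605; 1 − (1 − 0.546)/0.605 = 25%.
- High: 30% mortality, 8% return. k = 0.0594 + 0.08 = 0.1394, 9k = 1.255; 1 − (1 − 0.285)/1.255 = 43%.

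**All moves**

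A continuous-time Markov model (never in a nursing home, in one, returned home, dead) was read at discharge, month 3 and month 12. Each cell is the percentage of randomised patients; capture is in brackets.

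| Mortality; monthly return | True ever | Two calls only | Calls plus discharge destination |
|---|---|---|---|
| 15%; 0 | 13.78 | 12.55 (91%) | 12.95 (94%) |
| 20%; 3% | 13.53 | 10.85 (80%) | 11.74 (87%) |
| 25%; 3% | 13.28 | 10.29 (77%) | 11.30 (85%) |
| 30%; 8% | 13.02 | 8.41 (65%) | 10.07 (77%) |

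With discharge destination counted, the missed share runs from 100 − 94 = 6% to 100 − 77 = 23%. The result depends on the assumed 5%: if nobody went directly to a nursing home, capture would be 90% to 63%, so 10–37% would be missed.

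**Between arms (rows 2 and 3: same entry hazard, mortality 20% versus 25%)**

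- True gap: 13.53 − 13.28 = 0.25 points.
- Gap seen with discharge destination: 11.74 − 11.30 = 0.44. Artefact: 0.44 − 0.25 = 0.19.
- Gap seen from the calls alone: 10.85 − 10.29 = 0.56. Artefact: 0.56 − 0.25 = 0.31.

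The arm with more deaths looks less institutionalised by an extra 0.2–0.3 points. In the same rows the undercount within an arm is larger: 13.53 − 11.74 = 1.8 and 13.28 − 11.30 = 2.0 points with discharge destination, or 2.7 and 3.0 from the calls alone.

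**The case against.** **Relatives are a named source.** Section 4.2 says the information comes from patients or relatives, so a move before death could be reported. That stands as a reason to say such stays can be missed rather than that they are. It does not close the gap, because it names an informant and gives no question or field for moves since the last contact.

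**Annex 3 might fill the gap.** Sections 9.3 and 9.4 call for the economic evaluation at both calls, and the subject form asks for days in residential centres. A reader might infer that nursing-home time is lost from the economic analysis; the documents do not show that. Nor do they show it being collected: the form is headed baseline and no follow-up subject form is shown. If it were repeated at month 12, a six-month look-back would still leave months 3 to 6 uncovered. The supportable statement is that no follow-up field for nursing-home days is shown.

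**Permanent placement may be the real target.** Table 2 and section 10 agree on the word permanent, and if that is what is meant, temporary stays are not misses. This is fair, but section 4.2 says otherwise, and a permanent placement that ends in death before the next call would still have no field.

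**Differential bias.** A reader might infer a false treatment difference of several points. That would need nearly all entries to fall after month 3 and a large gap between arms in death after entry. The documents give no death rates, and discharge destination and the month-3 call catch the earlier moves.

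**Conclusion.** The point holds as a mismatch between definition and data collection. Following section 9 exactly cannot yield the outcome in section 4.2, and four places in the plan describe it in three ways. Under the assumed rates, about 6–23% of patients ever institutionalised would go unrecorded once discharge destination is counted, with the interval from month 3 to month 12 as the main exposure. The direction of any bias between arms is clear, with lower capture where more patients die, but its size is probably small.

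All magnitudes rest on assumptions; the textual mismatch does not. Institutionalisation is a secondary outcome, so the primary outcomes and the sample size are unaffected. The change should be made because dates not collected at the time are hard to recover later.

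**What to change.** 1. In 9.3, 9.4 and Table 2, replace the current-residence item with: *Any nursing-home stay since last contact (yes/no; date in, date out; temporary or permanent), and current residence.* Ask a relative when the patient has died.
2. In 4.2, define the outcome as any nursing-home entry from discharge to 12 months, including direct discharge to a nursing home and entries before death. This keeps the time origin at discharge, as 4.2 has it.
3. Derive the section 10 permanent rate from the same item through the permanent flag. State whether the Annex 3 residential-centre question is repeated at follow-up and over what look-back.
4. Reconcile the follow-up times in 7.2 (3 and 6 months) with section 9 (3 and 12 months).

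No visits are added. The cost is a few extra eCRF fields, one or two minutes per call, some recall error over nine months, and a short question to relatives of patients who have died.
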